4.1.2 Phase II

After RP2D is determined, a phase II study will be carried out to assess the anti-tumor activity of hu3F8-BsAb. Two groups of patients will be studied: Group 1 will consist of patients with relapsed or refractory NB and Group 2 of relapsed or refractory measurable osteosarcoma. Hu3F8-BsAb is given on Days 1 and 8 of each cycle. The duration of each cycle is 28 days. HAHA titer will be measured after each cycle. Extent of disease evaluation (EOD) will be performed after the second dose of cycle 2 and cycle 4, then every 3 months thereafter. A total of 4 cycles will be given, and patients with no life-threatening toxicity clearly attributable to hu3F8-BsAb, no PD, and continuing to meet all eligibility criteria have the option of receiving additional cycles up to 2 years from the start of the hu3F8-BsAb treatment. Patients may continue therapy beyond 4 cycles even if they achieve remission. For Group 1, the overall response rate will be evaluated and is defined as the proportion of patients achieving complete remission (CR) or partial response (PR) based on revised International Neuroblastoma Response Criteria (INRC) as the best response at the end of cycle 2 and cycle 4. (See Section 12). For Group 2, 4-month PFS will be assessed and is defined as the proportion of patients who have not developed PD at the end of 4 months from the first dose of Hu3F8-BsAb. In addition, we will determine the number of patients who have CR or PR as the best response at the end of cycle 2 and cycle 4. (see Section 12)

4.1.3 Phase I Dose-Escalation Schedule

The phase I dose-escalation schedule schema is summarized in Table 4 below. Dose Level 1 is the starting dose, and the escalation and de-escalation schedule are described in Section 9.1. DLTs are defined in Section 9.1.

Level	Dose on day 1	Dose on day 8	Dosage per cycle

Table 4Dose escalation schedule

4.2 Intervention

Phase I

Hu3F8-BsAb is given IV over \sim 1-3 hours on Days 1 and 8 for each cycle. In cycle 1, blood is drawn for PK studies as described in Section 9.1.4.

Phase II

Hu3F8-BsAb is given IV over ~1-3 hours on Days 1 and 8 for each cycle.

5 THERAPEUTIC/DIAGNOSTIC AGENTS

The investigational medicinal product is fully humanized bispecific antibody (hu3F8-BsAb).

Hu3F8-BsAb

The Sponsor, Y-mAbs, will provide hu3F8-BsAb 2 mg/mL solution for intravenous infusion. No other medicinal products or auxiliary medicinal products will be provided by Y-mAbs.

Hu3F8-BsAb drug product (DP) is manufactured in compliance with good manufacturing practice (GMP) regulations and no excipients of human or animal origin have been used. Final clinical DP formulation is a solution with 2 mg/mL hu3F8-BsAb buffered with sodium citrate dihydrate, citric acid monohydrate, and sodium chloride, and stabilized with Kolliphor P188 (Poloxamer 188). The final presentation is sterile filtered and filled into 2 mL vials.

Drug dilution and preparation procedure is provided in Appendix B.

6 CRITERIA FOR SUBJECT ELIGIBILITY

6.1 Subject Inclusion Criteria

6.1.1 Diagnosis

Phase I

- Patients must have either (1) a diagnosis of NB as defined by international criteria,⁷⁷ i.e., histopathology (confirmed by the MSKCC Department of Pathology) or BM metastases plus high urine catecholamine levels, or (2) high grade osteosarcoma verified by histopathology (confirmed by the MSKCC Department of Pathology), or (3) other GD2-expressing solid tumor.
- For tumors other than NB and osteosarcoma, only tumors known to be GD2 positive are eligible: melanoma, desmoplastic small round cell tumors, retinoblastoma, medulloblastoma, and soft tissue sarcomas including liposarcoma, fibrosarcoma, malignant fibrous histiocytoma, leiomyosarcoma, and spindle cell sarcoma. Patients with medulloblastoma are eligible only if they have metastatic disease outside the CNS (e.g. in the bone marrow)
- NB patients must have chemorefractory (e.g. refractory to standard induction chemotherapy including cyclophosphamide, vincristine, cisplatin, etoposide) or relapsed high-risk (HR) neuroblastoma. HR NB is defined as *MYCN*-amplified stage 3/4/4S of any age, or *MYCN*-nonamplified stage 4 in patients > 18 months of age at diagnosis.
- Osteosarcoma patients must have relapsed or refractory osteosarcoma after receiving standard systemic chemotherapy (e.g. combination methotrexate, doxorubicin, and cisplatin [MAP]).
- For non-NB and non-osteosarcoma tumors known to be GD2(+), patients must have relapsed or refractory disease that is resistant to standard therapy.

Phase II

- Group 1:
 - NB patients must have chemo refractory or relapsed HR NB. HR NB is defined as *MYCN*-amplified stage 3/4/4S of any age, or *MYCN*-nonamplified stage 4 in patients > 18 months of age at diagnosis.
 - The diagnosis of NB must be defined by international criteria⁷⁷ i.e., histopathology (confirmed by the MSKCC Department of Pathology) or BM metastases plus high urine catecholamine levels.
- Group 2:
 - Patients must have a diagnosis of high grade osteosarcoma defined by histopathology (confirmed by the MSKCC Department of Pathology).

• Patients must have relapsed or refractory osteosarcoma after receiving standard systemic chemotherapy (e.g. combination methotrexate, doxorubicin, and cisplatin [MAP]).

All criteria below are common to both phase I and phase II:

6.1.2 Disease status

- For NB patients, patients must have measurable or evaluable disease (e.g. abnormal findings in computed tomography (CT), magnetic resonance imaging (MRI), metaiodobenzylguanidine (MIBG) scan, or positron emission tomography (PET)) OR morphologic evidence of disease in bone marrow.
- For osteosarcoma or other GD2(+) solid tumor patients, patients must have measurable disease. (See Section 12.4 for a definition of measurable disease)

6.1.3 Other criteria

- Patients must be ≥ 1 year of age and < 18 years of age.
- Patients with prior exposure to anti-GD2 antibodies must have a negative HAHA antibody titer .
- Adequate hematopoietic function defined as:
 - Absolute neutrophil count \geq 500/ul
 - Absolute lymphocyte count \geq 500/ul
 - Platelet count $\geq 25,000/\text{ul}$
- Negative serum pregnancy test in women of child-bearing potential.
- Women of child-bearing potential must be willing to practice an effective method of birth control while on treatment.
- Signed informed consent indicating awareness of the investigational nature of this program.

6.2 Subject Exclusion Criteria

- Patients who are in complete remission.
- Existing severe major organ dysfunction. i.e. renal, cardiac, hepatic, neurologic, pulmonary, or gastrointestinal toxicity ≥ Grade 3 except for hearing loss, alopecia, anorexia, nausea, hyperbilirubinemia or hypomagnesemia from TPN, which may be Grade 3.
- Hematologic and active CNS malignancies including CNS metastasis.
- Active life-threatening infection.
- Pregnant women or women who are breast-feeding.

- Inability to comply with protocol requirements.
- History of autoimmune disease with potential CNS involvement or a current autoimmune disease.
- Chemotherapy or immunotherapy within three weeks prior to study enrollment. T-cell based immunotherapies (e.g. CAR-modified T cells, checkpoint inhibitors) should have been completed >6 weeks prior to treatment with hu3F8-BsAb.

7 RECRUITMENT PLAN

Patients will be offered participation in this study by their attending physician in the Department of Pediatrics at Memorial Sloan Kettering Cancer Center *only*. Patients will be offered the opportunity to participate if they have relapsed or refractory high-risk NB, osteosarcoma, or GD2 (+) tumor as defined in Section 6.1. No patient will be identified by chart review or direct advertising. The consenting physician will be responsible for explaining the study, obtaining written informed consent and registering the patient on study. Patients of both genders and all ethnic backgrounds are eligible for this study.

Up to 30 patients will enroll in Phase I and up to 64 patients will enroll in Phase II.

8 PRETREATMENT EVALUATION

Pretreatment evaluations should be completed within 30 days of start of treatment. Echocardiogram and electrocardiogram can be completed within 45 days prior to treatment. All pretreatment evaluation should be performed after the completion of prior chemotherapy or immunotherapy.

- 1. Complete history and physical examination.
- 2. Blood pressure measurement (standing, sitting and lying down).
- 3. Complete blood count, serum creatinine, blood urea nitrogen, serum aspartate aminotransferase, serum alanine aminotransferase, serum alkaline phosphatase, serum total bilirubin, albumin, sodium, potassium, chloride, bicarbonate, magnesium, phosphate, ferritin, and C-reactive protein (CRP).
- 4. Echocardiogram (ECHO)
- 5. Electrocardiogram
- 6. Phase I only: C3 and CH50
- 7. Phase I only: Urinalysis.
- 8. Serum for analysis of HAHA if applicable (i.e., for patients previously treated with anti-GD2 antibodies). If the patient was previously treated with an antibody, any HAHA result since last antibody treatment can be used.

- 9. Blood for baseline cytokine studies (including IFN-y, IL-6, IL-8, IL-10).^{78,79}
- 10. Blood for baseline lymphocyte subsets (including CD3, CD4, CD8, Foxp3, CD127, CD45RA, CCR7) and T cell activation/exhaustion markers (including CD25 and PD-1).
- 11. For NB patients, BM aspirates and biopsies from bilateral iliac crests for morphology and detection of minimal residual disease.
- 12. Imaging by computed tomography (CT) or magnetic resonance imaging (MRI) of primary tumor site and/or known site(s) of relapse (if applicable), or PET scan, Bone scan, and/or MIBG scan (if the patient has neuroblastoma), or other diagnostic imaging as appropriate for specific disease.
- 13. Pregnancy test, if applicable, within 2 weeks of treatment.

9 TREATMENT/INTERVENTION PLAN

- 9.1 Phase I
- 9.1.1 General Outline

During phase I approximately 0.5 ml of the first Bs-Ab infusion will be collected about half-way through the infusion and assayed in Neuroblastoma research laboratory to determine quantity of hu3F8-BsAb in the final infusion product. In cycle 1, blood is drawn for PK studies as described in Section 9.1.4. Patients are admitted for dose 1 of cycle 1 of treatment and will be inpatient for approximately 4 days (minimum 48 hours) though the duration of stay may change if clinically indicated. Subsequent doses can be administered inpatient or outpatient. Patients are monitored for DLT clinically with physical examination, CBC and complete chemistry until Day 28. Patients with DLT will come off treatment HAHA titer is measured after each cycle. HAHA draws require about 5mL of serum. If HAHA develops, cycles are deferred for up to 4 months until HAHA titer until <1300 U/ml. Extent of disease evaluation will be performed after the second dose of hu3F8-BsAb in cycle 2 and cycle 4, every 3 months thereafter. (Table 6) A total of 4 cycles will be given.

Patients with no life-threatening toxicity clearly attributable to hu3F8-BsAb, no PD, and continuing to meet all eligibility criteria (with subsequently explained exceptions) have the option of receiving additional cycles up to 2 years from the start of the hu3F8-BsAb treatment. Inclusion criteria that no longer apply for patients to receive subsequent cycles are: disease status, since patients achieving remission may continue; and prior T cell immunotherapy timing restrictions, since all patients will have received Cycle 1 of hu3F8-BsAb. Even patients who achieve remission may continue therapy beyond

4 cycles. DLT and dose-schedule are described in Section 9.1.2 and 9.1.3. After cycle 2, intra-patient dose escalation will be permitted i.e. patients can receive the highest dose that has been evaluated and proven safe by DLT assessment. Patients will be admitted for at least 48 hours for their first escalated dose.

The treatment and evaluation schedule may require minor adjustment as clinically indicated or due to circumstance (e.g. due to PDH closure for holidays or due to inclement weather).

9.1.2 Dose-Escalation Plan and Dose Limiting Toxicity (DLT)

9.1.2.1 Dose-Escalation Plan

This is a Phase I trial to determine the MTD of hu3F8-BsAb that leads to DLT in approximately 15% of patients. Hu3F8-BsAb is dosed based on body weight (BW) rather than body surface area (BSA). Unlike chemotherapy for which clearance ultimately depends upon cardiac output which is dependent upon BSA, antibody distribution and clearance depend on total blood volume which is determined not by BSA, but by BW. Dose escalation will start at dose level 1, 0.0045 mcg/kg/dose (0.009 mcg/kg/cycle). Dose-escalation will be performed in two stages. In the first stage, the trial will accrue 1 patient per dose until the first \geq Grade 2 toxicity (except for Grade 2 sinus bradycardia, sinus tachycardia, fever, nausea, vomiting, diarrhea, urticaria, headache, paresthesia, electrolyte disturbances, pain) is encountered. The subsequent dose allocation will follow the Continual Reassessment Method (CRM). CRM assumes a simple model for the probability of a DLT as a function of dose, and uses the occurrence of toxicities in the patients enrolled in the trial to sequentially determine which dose to administer to a new patient. Patients will be assigned at each dose one at a time. New subjects will be allocated a dose as suggested by the CRM algorithm based on the toxicities of previously accrued patients. If DLT data are not available for the previously accrued 1 or 2 patients, the CRM will proceed with the dose as calculated with available toxicities/data, however if there are 3 enrolled patients with incomplete /outstanding DLT data, accrual will be paused. DLT data from at most 2 patients can be pending but no more than 2 patients are allowed to have incomplete DLT data. To protect patient safety, a dose escalation of more than one dose level is not permitted. We will examine 12 dose levels. (Table 4) Our initial estimates of DLT probabilities are: 0.001, 0.005, 0.01, 0.025, 0.05, 0.075, 0.10, 0.15, 0.25, 0.35, 0.45, 0.50 for doses 1-12, respectively. Thus, our a priori belief is that dose level 8 is the MTD. We assume that the dose- toxicity follows a hyperbolic tangent model P(DLT=yes at dose d)=($(\tanh d+1)/2$)^a, where a is the unknown parameter that we need to estimate in order to determine which dose is the MTD.A value of a=1.0 indicate that our prior beliefs were correct; while a value of a less than (greater than) 1.0 indicates that the combinations are more (less) toxic than believed. To reflect the uncertainty in our prior probability estimates, we assume it follows an exponential distribution (prior distribution) with mean 1.0. Dose escalation will be guided by the model after the occurrence of the first DLT. At that time, the above initial estimates of DLT might be revisited before model initiation to reflect the current knowledge on the safety profile and dose levels based on the observed data. We will enroll 30 evaluable patients. All patients who are enrolled in the study and receive their assigned dose are considered evaluable for toxicity. Additional subjects will be enrolled to replace any subjects who are enrolled, but do not receive treatment. In the

unlikely event that patient stops the drug due to HAHA before completing the first cycle, this patient will be considered inevaluable and will be replaced. If life-threatening toxicity occurs in any patient, further accrual at that dosage will be stopped pending review by the Principal Investigator (PI) or Co-PI. Toxicity at each dosage level is evaluated during the 28 days following the first dose of hu3F8-BsAb. No more than two patients will receive their first dose of hu3F8-BsAb within a 24 hour period. If no DLT is observed up to dose level 12 during the initial patient per dose escalation (e.g. no MTD), the RP2D will be determined as a minimum dose that gives the highest hu3F8-BsAb serum levels based on the PK data.

9.1.2.2 Dose Limiting Toxicities

Toxicity will be monitored using CTCAE version 4.0. DLT only during cycle 1, i.e. Days 1 through 28. Allowance will be made for the expected toxicities of hu3F8 from which hu3F8-BsAb was derived. (See Section 11.2). As stated above, in the first stage (1 patient per dose-level) dose-escalation will be performed until \geq Grade 2 related toxicity (except for Grade 2 sinus bradycardia, sinus tachycardia, urticaria, fever, nausea, vomiting, diarrhea, urticaria, headache, paresthesia, electrolyte disturbances, pain) is encountered, then the subsequent dose allocation will follow the CRM.^{75,76}

During the CRM phase, any \geq Grade 3 toxicity attributable to hu3F8-BsAb will be considered doselimiting with the following exceptions:

- Grade 3 cytokine release syndrome (CRS) improving to ≤Grade 1 CRS within ≤72 hours after starting systemic steroids (See Section 11.3 for a grading system and algorithm)
- Grade 3 pain improving to \leq Grade 2 within \leq 72 hours of its onset. Grade 3 pain associated with myalgia is an expected clinical toxicity associated with cytokine release syndrome (CRS).
- Grade 3 neutropenia or anemia
- Grade 3 thrombocytopenia without clinically significant bleeding.
- Grade 4 lymphopenia
- Grade 3 elevations of AST, ALT if they return to <Grade 3 by day 28
- Catheter related infections
- DLT of hypertension is defined as persistent hypertension higher than 99th percentile for >48 hours.

The following Grade 3 toxicities are related to infusion of monoclonal antibodies and will not be considered DLT if they resolve to <Grade 3 within 24 hours:

- Allergic reactions controlled with supportive care measures
- Vasovagal reaction
- Sinus bradycardia

- Sinus tachycardia
- Urticaria (improved to at least Grade 2)
- Fever

The following Grade 3 toxicities will not be considered a DLT if they resolve within 48 hours:

- Nausea
- Vomiting
- Diarrhea
- Peripheral neuropathy (paresthesia)
- Electrolyte disturbances

In all other cases, DLT is defined as Grade 3 or greater toxicities occurring during cycle 1 with the exception of toxicities clearly related to disease activity or co-interventions.

9.1.3 Criteria for continuing on therapy beyond cycle 1.

If patients experience DLT as described above, they will discontinue treatment. Patients will need to fulfill all eligibility criteria before each cycle. However, patients can continue treatment without delay if they have \leq grade 4 lymphopenia. Cycles 2-4 may be delayed due to toxicities other than DLT for a maximum of four weeks i.e. maximum duration between dose 1 of the prior cycle and dose 1 of the next cycle can be \leq 56 days. If HAHA titer of >1300 U/ml develops, cycles beyond cycle 1 may be delayed for up to 120 days. However, if the duration between cycles is >28 days, patients will be required to undergo extent of disease evaluation to ensure that there is no progressive disease.

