The CRM report includes summary and detailed toxicity information and the recommended next dose level (determined by the CRM program). The report will normally be generated by the CRC; however other members of the research team can be given access to run the CRM module. The dose level for new patients is not automatically saved. The PI must check the report to determine if all toxicity data are correct and up-to-date. If the data are correct, the PI will acknowledge this and sign the last page of the report which displays the recommended dose assignment. The last page of the report also contains space to fill in the MRN and name of the newly registered patient who is to receive this dose assignment. The CRC will enter the dose level in CTMS after a patient is registered.

If any data are incomplete or incorrect, the PI will inform the CRC. The CRC will correct the data and indicate to the PI when this is done. The CRDB CRM module will be run again to determine the next patient's dose level. The report will be generated and the PI will be notified to approve the assignment. The dose level will then be entered into CTMS.

Although both children and adults are eligible for enrollment on this study, we do not anticipate any significant differences in target specific toxicity between adults and children based on our experience of over 780 children under age 12 and over 100 patients over age 12 (including >50 over age 18) in the past 20 years with m3F8 and hu3F8. Additionally, there are no reported significant differences in the toxicity of blinatumomab in children compared to adults; 65 thus children and adults will be enrolled and evaluated simultaneously on each dose level.

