16.2 Data and Safety Monitoring

A Data Monitoring Committee (DMC) is established to assure patient safety and will function independently of all other individuals associated with the conduct of the trial, including site investigators participating in the trial. The DMC will consist of a minimum of 2 physicians whose expertise covers relevant specialties and, where applicable, a statistician.

During the conduct of Phase I the DMC will evaluate available safety information and recommend trial continuation or termination. If continuation is recommended, the DMC will recommend to the sponsor whether the dose should be escalated, de-escalated, or held at the same level based on the CRM.

At the completion of Phase I, the DMC will review relevant data and provide a recommendation regarding the MTD and RP2D.

During the conduct of Part 2, DMC meetings will be held on a regular basis to review cumulative safety data and evaluate whether the trial should be modified, stopped, or continue unchanged. The Sponsor Safety Committee will evaluate the recommendations from the DMC after each DMC meeting. Any significant finding/recommendation from the DMC and endorsed by the Sponsor Safety Committee will be communicated to the regulatory authorities and Institutional Review Board (IRB)/Ethics Committee (EC) as appropriate, and to the sites.

Responsibilities, procedures, content of the DMC packages, and workflow of the DMC are specified in the DMC Charter.

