17.2 Adverse Event (SAE) Reporting

17.2.1 Definition of Adverse Events

An AE is any untoward medical occurrence in a patient administered a pharmaceutical product which does not necessarily have a causal relationship with the treatment.

An AE can, therefore, be any unfavorable and unintended sign (including an abnormal laboratory finding), symptom, or disease temporally associated with the use of a product, whether or not considered related to the product.

An AE includes:

- A clinically significant worsening of a concomitant illness.
- A laboratory abnormality which is clinically significant, i.e. an abnormality that suggests a disease and/or organ toxicity and is of a severity that requires active management. Active management includes interventional treatment or further investigations, for example change of medicine dose or more frequent follow-up due to the abnormality.

Pre-existing condition, (i.e., a disorder present before the AE reporting period started and noted on the medical history/physical examination form) should not be reported as an AE unless the condition worsens, or episodes increase in frequency during the AE reporting period.

Diagnostic and therapeutic non-invasive and invasive procedures, such as surgery, should not be reported as AEs. A medical condition for which an unscheduled procedure was performed should, however, be reported if it meets the definition of an AE. For example, an acute appendicitis should be reported as the AE and not the appendectomy.

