6.7.2. DLT for Phase I

A DLT is defined as one or more events occurring during cycle 1. For more details, see Section 2.1.1.5.

A summary table of DLTs by treatment group occurring during cycle 1 will be provided, presenting the number and percentage of patients with DLTs, the number of DTLs per patient, and the type of DLTs in patients of phase 1 from the safety DLT Evaluable Analysis Set.

A by-patient listing of DLTs that occur during cycle 1 is planned by treatment group and for all patients from the DLT Evaluable Analysis Set during phase I of this trial. Patients will be grouped by the treatment group to which they are originally assigned, including those who may receive subsequent treatment at a lower or higher dose level.

Patients with and without DLTs from the DLT Evaluable Analysis will be plotted in a graph with dose level on the vertical axis and patient number (patient id sorted in the order in which they received the first dose) on the horizontal axis.

MTD will initially be estimated as the next suggested dose level from the CRM model described above based on all data in the DLT analysis set. This corresponds to the dose level with a posterior probability of DLT that comes closest to the toxicity level of 0.15.

Final MTD is determined by the DMC and the safety group, as other safety data than the DLTs may be relevant

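### The DLT exception names only Grade 4 lymphopenia, so as written Grade 3 lymphopenia is dose-limiting and the more severe Grade 4 is not

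*Protocol*

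**What the plan says.** Protocol 9.1.2.2 sets a general rule for the CRM phase: a toxicity of Grade 3 or higher attributable to hu3F8-BsAb is dose-limiting unless it is excepted. The exceptions that concern blood counts are "Grade 3 neutropenia or anemia", Grade 3 thrombocytopenia without clinically significant bleeding, and "Grade 4 lymphopenia". Lymphopenia appears nowhere else in the section, including the lists of Grade 3 events excused if they resolve within 24 or 48 hours. The section closes with a residual rule: "In all other cases, DLT is defined as Grade 3 or greater toxicities occurring during cycle 1", apart from events clearly related to disease activity or co-interventions.

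SAP 2.1.1.5 repeats the list and the residual rule. SAP section 7, which records departures from the protocol, changes the MTD definition and the DLT-evaluable set but leaves this bullet alone.

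Protocol 9.1.3 and SAP 2.1.1.6 say that a patient with a DLT discontinues. They also say that "patients can continue treatment without delay if they have" lymphopenia up to and including Grade 4.

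**The concern.** A DLT definition should not penalise the milder grade of an event and excuse the more severe grade. This one does, and nothing in the DLT section tells the reader to extend the Grade 4 exception down to Grade 3.

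The event was foreseen. The protocol wrote both a lymphopenia exception and a lymphopenia continuation waiver, and Protocol 10.3 schedules cycle 1 blood counts at about Days 2, 5, 8, 15 and 28.

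Two things are at stake. Cycle 1 DLT is the Phase I primary variable (SAP 2.4.1) and the toxicity data that the CRM uses, so a Grade 3 lymphopenia scored as a DLT lowers the recommended dose. Protocol 13.2 also takes a patient with a cycle 1 DLT off treatment.

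**Working it through.** **1. The text applied to each grade.** The event is an attributable lymphopenia in cycle 1 of the CRM phase.

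| Provision | Grade 3 | Grade 4 |
|---|---|---|
| General rule, 9.1.2.2 | DLT unless excepted | DLT unless excepted |
| Exception list | not listed | listed |
| Residual clause | DLT | not reached |
| Result | DLT | not a DLT |
| 9.1.3, DLT rule | discontinue | does not apply |
| 9.1.3, lymphopenia waiver | continue without delay | continue without delay |

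The severity order is inverted. For Grade 3, the two rules in 9.1.3 also give opposite instructions. Excepting both grades removes both problems.

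**2. Effect on the next dose (illustration only).** The plan gives no figure to reproduce.

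Inputs:
- Initial DLT estimates p for levels 1 to 12: 0.001, 0.005, 0.01, 0.025, 0.05, 0.075, 0.10, 0.15, 0.25, 0.35, 0.45, 0.50 (Protocol 9.1.2.1).
- Model P(DLT at level d) = p_d^a, with a exponential, mean 1; target 0.15; no escalation of more than one level (Protocol 9.1.2.1).
- Doses per cycle from SAP Table 5.
- Assumed data: one patient on each of levels 1 to 8, plus one extra on level 4, because Protocol 14.1.1 reports five patients on levels 1 to 4. The only event is one Grade 3 lymphopenia, at level 8.

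Posterior of a ∝ exp(−a) × Π(1 − p_i^a) over patients without a DLT × p_8^a if the level 8 event counts as a DLT. The plug-in rule puts the posterior mean of a into p_d^a and picks the level closest to 0.15.

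- **Not a DLT:** mean a = 1.78. Level 10 gives 0.35^1.78 = 0.154, the closest. The one-level limit makes the assignment level 9 (81.3 mcg/kg/cycle).
- **Scored as a DLT:** mean a = 0.89. Level 7 gives 0.10^0.89 ≈ 0.130, a distance of 0.020. Level 8 gives 0.15^0.89 ≈ 0.186, a distance of 0.036. The assignment is level 7 (21.3 mcg/kg/cycle).

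The picks do not change if the extra patient is on level 1, 2 or 3. They also do not change if a Grade 2 toxicity without a DLT had already started the CRM: after each of levels 4 to 8 the model picks 9 or 10, and the limit allows one level up each time.

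**3. Recovery.** After one DLT-free patient, mean a = 0.94, level 8 is estimated at 0.167 and the pick is level 8. After six, mean a = 1.21, level 9 is estimated at 0.187 and the pick is level 9.

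**4. The same single case at other levels (plug-in rule).**

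| Level of the event | Next level if DLT | Next level if not | Gap |
|---|---|---|---|
| 5 | 5 | 6 | 1 |
| 6 | 5 | 7 | 2 |
| 7 | 6 | 8 | 2 |
| 8 | 7 | 9 | 2 |
| 9 | 8 | 10 | 2 |

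**5. The other selection rule.** The SAP speaks of the posterior probability of DLT closest to 0.15, which could also mean the posterior mean of p_d^a. Under that rule the level 8 case drops to level 6. Return to level 8 takes four DLT-free patients and level 9 takes ten. The plug-in rule therefore gives the smaller drop.

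**The case against.** The best defence is that the intent is plain. Protocol 9.1.3, directly after the DLT list, lets patients continue with lymphopenia up to Grade 4, and only a reading that excuses both grades makes the two sections agree. That is good evidence of intent and of how the site would probably score the event. It does not amend the DLT definition, and the clash it exposes is itself a reason to correct the bullet.

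The neighbouring bullets settle little. "Grade 3 neutropenia or anemia" shows that naming a lower grade does not excuse a higher one. Because Grade 3 is the lowest grade that can be a DLT, it cannot show whether excusing Grade 4 also excuses Grade 3. The case rests on the missing Grade 3 entry and the residual clause.

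Several filters stand between the wording and a wrong dose:
- The event must be attributable and must peak at Grade 3, since Protocol 17.2.5.4 records the worst grade.
- Protocol 17.2.1 makes a low count an adverse event only if it is "A laboratory abnormality which is clinically significant", meaning severe enough to need active management.
- Before each assignment, "The PI must check the report to determine if all toxicity data are correct and up-to-date" (Protocol 14.1.1.2).
- On continuation, "the DMC will recommend to the sponsor whether the dose should be escalated", de-escalated or held (Protocol 16.2).
- SAP 6.7.2 adds: "Final MTD is determined by the DMC and the safety group, as other safety data than the DLTs may be relevant".
- Protocol 11.6 allows treatment stopped for toxicity to resume once eligibility is met again, although how this fits with the DLT stop rule is unclear.

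These make harm less likely. They do not correct the rule that the PI and the DMC are asked to apply, and no document shows a case actually scored this way.

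**Conclusion.** The exception is wrong as written in both documents: it inverts severity for lymphopenia in the Phase I primary endpoint. The direction is toward lower doses and a lower MTD. The size cannot be stated because no lymphopenia rate is given and none is assumed here.

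The illustration shows what one classification can do to one assignment: level 7 and not level 9 under the plug-in rule, or level 6 under the posterior-mean-probability rule. It rests on an assumed patient sequence and on the initial DLT estimates, which the protocol allows to be revisited before the model starts. It shows no bias in the final MTD, and under the plug-in rule one DLT-free patient returns the assignment to level 8. The intent is probably to tolerate both grades. The point is a drafting error that should be corrected, with a possible but not certain effect on dosing.

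**What to change.** In Protocol 9.1.2.2 and SAP 2.1.1.5, change the bullet to *Grade 3 or 4 lymphopenia*. Protocol 9.1.3 needs no change, since its waiver then agrees with the DLT definition.

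Before the next CRM run, check the accrued cycle 1 records for any Grade 3 lymphopenia scored as a DLT. Refer any such case to the DMC before it is reclassified.

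The cost is one bullet in each document and one check of the DLT records.
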